**Table 5–4: First Supplementary Estimand: ICEs and Strategies to address them**

ICEs**	Reason for ICE	Strategy	Data handling method
Temporary Treatment interruption*	AEs (treatment related/unrelated)	Treatment policy	Utilise the collected data after ICE.
	COVID-19 and administrative reasons	Hypothetical, If participant complied with treatment.	Model outcomes during the ICE under the hypothetical scenario.
Permanent discontinuation of randomized treatment	AEs (treatment related/unrelated) or Lack of efficacy		
	For participants who remained untreated/on background therapy.	Treatment policy	Utilise the collected data after ICE.
	For participants who initiate alternative VMS treatment	Hypothetical, If participant remained untreated.	Model outcomes after the ICE under the hypothetical scenario.
	Other treatment-unrelated reasons, including COVID-19	Hypothetical, If participant did not discontinue the randomized treatment.	Model outcomes after the ICE under the hypothetical scenario.
Intake of prohibited concomitant medication having impact on efficacy	All reasons	Hypothetical, If participant did not take prohibited concomitant medication.	Model outcomes under the hypothetical scenario during the period of confounding.

ICE=Intercurrent event, AE=Adverse event, VMS = Vasomotor symptoms

\*Definition of temporary treatment interruption:

Week 1 = Treatment taken on <5/7 days during week 1.

Week 4 = Treatment taken <80% during weeks 1-4 OR treatment taken on <5/7 days during either week 3 or 4.

Week 8 = Treatment taken <80% during weeks 1-8 OR treatment taken on <5/7 days during either week 7 or 8.

Week 12= Treatment taken <80% during weeks 1-12 OR treatment taken on <5/7 days during either week 11 or 12.

\*\*ICEs will be reviewed prior to the study unblinding.

The details of data handling and missing data imputation for the first supplementary analysis of the primary endpoints are summarized in the [Table 5–5](#). A pattern-mixture model using multiple imputation (MI) will be used to impute missing or discarded values that occur in presence of ICEs in a way that aligns with the ICE strategies.

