**Table 5-5: First supplementary analysis data handling and missing data imputation strategy.**

Pattern ID	ICE and the associated reason	ICE strategy and data handling	Reference group for modeling the distribution of missing or unobservable data
1	Intake of prohibited medications	Hypothetical strategy If participant did not take prohibited concomitant medication.	Participants, from the same arm, who comply** with treatment regimen and have observed data at the time point that requires imputation.
	Any reason	Discard the collected data after the intake of prohibited medication(s) for a certain time frame based in the medication class (See Section 6.5.3 for details).	
2	Temporary treatment interruption*  Due to COVID-19/ administrative or any other treatment unrelated reasons	Hypothetical strategy If participant complied with treatment.  Data collected for a specific assessment during/after a temporary treatment interruption will be discarded for that assessment Week only.	Participants, from the same arm, who have available data before and during the treatment interruption.  MI will be used to model change from a time point before treatment interruption to a time point with treatment interruption (Copy Increment from Reference imputation strategy).
3	Permanent treatment	Treatment policy/Hypothetical	Missing values that occur after the ICE will be

	discontinuation  Due to AE/lack of efficacy	strategy  If participant remained untreated/on background therapy after permanent discontinuation of the randomized treatment, use the treatment policy strategy and utilize the collected data.  Otherwise, if participant initiated an alternative treatment, use the hypothetical strategy under the hypothetical scenario “If participant did not initiate an alternative treatment after permanent discontinuation of randomized treatment”. Discard data after the ICE.	imputed using a similar MI model as used in the main analysis of the primary endpoint, i.e., the MI regression model will include auxiliary variables indicating (yes/no) whether the participant continued on randomized treatment at each visit ( Guizzaro et al., 2021 ).

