4	Permanent treatment discontinuation  Due to COVID-19/ administrative or any other treatment unrelated reasons	Hypothetical strategy If participant did not discontinue the randomized treatment due to the specified reason.  Any data collected after permanent treatment discontinuation will be discarded.	All other participants from the same arm (i.e., participants without a similar ICE at the time point that requires imputation).

\*If more than one interruption for different reasons is recorded during the specified weeks (please see the definition of ICE in Section 1.1), the data handling rule and missing data imputation will be performed based on the reason in the following pre-specified order: 1) AE, 2) Due to COVID-19/ administrative or any other treatment unrelated reasons.

\*\* Complying with treatment regimen is defined as having no ICEs (i.e., no early discontinuation of randomized treatment, no treatment interruption in the respective week (definition in [Table 1–2](#)) and no intake of prohibited concomitant medications.

Missing values that occur in the time frame outside of any identified ICE and simply represent missed assessments will be assumed missing at random (MAR). Such missing values are likely to be intermittent and will be imputed using a Monte Carlo Markov Chain (MCMC) MI method for imputation of non-monotone missing data. Additional details are provided in Section 6.3.

A pattern-mixture model using multiple imputation will be applied to impute missing and unobservable data to mimic the distribution of observed data in the appropriate reference group as described in [Table 5–5](#), conditional on covariates and partially observed data. The imputations will be done sequentially in patterns 1 through 4. The reference group for imputation in patterns 3 and 4 may contain participants who have some values imputed during the imputation of preceding patterns. Consequently, the MI model for pattern 4 will reflect a mixture of participants, some of which fully comply with the randomized treatment and some with other types of ICEs. Additional details of the pattern-mixture modeling with multiple imputation are provided in Section 6.3.

Each imputed dataset will be analyzed using the MMRM model specified in [Table 5–3](#) to obtain an estimate of the treatment effect. The results will be combined using the Rubin’s rule ([Rubin, 1987](#)) to obtain an overall estimated treatment effect.

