### 6.3 Appendix 3: Pattern-mixture modeling approach for supplementary analyses

A pattern mixture modeling approach (Little, 1993) will be used in combination with multiple imputation (Ratitch B, O'Kelly M; Guizzarro et al., 2021) to handle missing and unobservable data that occur in presence of ICEs in a way that aligns with the estimand strategy for each type of ICE.

We will use a reference-based pattern imputation approach which makes use of observed data from the reference group for estimating the multiple imputation model for each pattern that requires distinct assumptions about a plausible distribution of missing/unobservable data. The reference group consists of participants who are expected to have similar outcomes to those with missing/unobservable values after conditioning on baseline covariates, partially observed data and, in some cases, indicators (yes/no) for whether participants remained on the randomized treatment at each visit. Pattern definitions and the corresponding reference groups that will be used for the supplementary analysis of the primary endpoints are specified in Table 5–5 and Table 5–7. Multiple imputation models will be estimated for frequency of hot flashes (referred to by the generic term “outcome” below).

The pattern-mixture multiple imputation and analysis method will be implemented by a series of steps using SAS PROC MI, MIXED, and MIANALYZE:

1. **Imputation:** Impute missing and unobservable values at baseline, Week 1, 4, 8 and 12 (see [Table 5–5](#) and [Table 5–7](#) for definition of patterns):

**Impute intermittent (non-monotone) missing values that occur outside of the time frame of any ICE as well as missing and unobservable values that occur in presence of ICEs in pattern 1.**

A joint multivariate normal multiple imputation model will include outcomes at baseline, Week 1, 4, 8 and 12, as well as the fixed, categorical effects of treatment and region.

This step will be implemented using PROC MI with the MCMC statement and the following options: “CHAIN = MULTIPLE”, and “SEED = 21810” to produce 500 imputed datasets. The input dataset will contain all participants with missing/unobservable data targeted by this step as described above and participants from the reference group, i.e., participants who complied with the randomized treatment. Partially imputed data will serve as input to complete imputation in patterns 3 and 4.

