**Impute missing and unobservable data occurring after an ICE associated with pattern 3.**

Missing values that occur after the ICE will be imputed using a similar MI model as used in the main analysis of the primary endpoint. That is, the MI monotone regression model (PROC MI with MONOTONE REG statement) will include auxiliary variables indicating (yes/no) whether the participant continued on randomized treatment at each visit ([Guizzarro et al., 2021](#)) in addition to baseline value, values at previous time points, and the fixed, categorical effects of treatment and region. In case there are less than 10 participants (who permanently discontinued the randomized treatment) across both treatment groups with available post-discontinuation data at any intermediate time point, the indicator variable will not be

included in the imputation model for that time point. The input dataset will include all participants in the analysis set, including their observed values post premature treatment discontinuation and values that might have been imputed as part of pattern 1 and 2. Prior to this step, intermittent missing values in the input dataset will be partially imputed using PROC MI with the MCMC statement using multiple chains.

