**Table 6–3: Preliminary list of alternative VMS treatment by drug grouping (can be updated during blind review meeting)**

DGCODEL0	DGNAME0	DGCODEL1	DGNAME1	DGCODEL2	DGNAME2	Duration of impact with respect to efficacy* (considered up to 12 weeks**)
		5	Hormone replacement therapy	2	Oestrogens	1, From 1st dose to 4 weeks after the last dose if the route is vaginal, intravaginal, cutaneous, nasal or transdermal. 2, From 1st dose to 8 weeks after the last dose if the route is oral, sublingual or intrauterine, 3, From 1st dose to 12 weeks or longer if the route is subcutaneous or intradermal.
		5	Hormone replacement therapy	3	Progestogens	1, From 1st dose to 4 weeks after the last dose if the route is vaginal, intravaginal, cutaneous, nasal or transdermal. 2, From 1st dose to 8 weeks after the last dose if the route is oral, sublingual or intrauterine, 3, From 1st dose to 12 weeks or longer if the route is subcutaneous or intradermal.
1633	Drugs for psychiatric disorders	111	Antidepressants	113	Selective serotonin reuptake inhibitors (SSRI)	From 1st dose to 4 weeks after the last dose

\*In this column, the terms "1st dose" and "last dose" both refer to the start date and stop date of certain doses of concomitant medication. If the dose was changed, a new start date and/or stop date were reported.

\*\* No further differentiation if duration of impact is longer than 12 weeks since ICEs are considered in the analysis only for the first 12 weeks of the study.

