### 6.5.3 Intake of prohibited concomitant medication having impact on efficacy

Drug groupings, individual drugs and manual review will be used to identify prohibited concomitant medications that were defined in the protocol to influence efficacy. All here listed drug groupings/names were reported in OASIS 1-3 studies, although other medications may also be prohibited per the protocol.

In terms of the efficacy endpoints related to the change from baseline in HF frequency

1. Any intake of prohibited medication during Week 1 that has an effect on HF will be considered an intercurrent event.
2. For weeks 4, 8, and 12, not only intake in the respective week but also, intake that occurred prior to Week 4, 8, and 12 should be considered as an intercurrent event if within the washout period of the prohibited drug.

The list of prohibited concomitant medication with the pre-defined washout period for their effect will be reviewed during blind review of the data and finalized prior to unblinding.

**Table 6–5: Preliminary list of prohibited concomitant medication by drug grouping (can be updated during blind review meeting)**

DGCODEL0	DGNAME0	DGCODEL1	DGNAME1	DGCODEL2	DGNAME2	Duration of impact with respect to efficacy* (considered up to 12 weeks**)
		108	Drugs acting on gonadotropin-releasing hormone (GnRH) receptors	109	GnRH agonists	From 1st dose to 12 weeks after the last dose
		108	Drugs acting on gonadotropin-releasing hormone (GnRH) receptors	110	GnRH antagonists	From 1st dose to 12 weeks after the last dose
		5	Hormone replacement therapy	2	Oestrogens	1, From 1st dose to 4 weeks after the last dose if the route is vaginal, intravaginal,

						cutaneous, nasal or transdermal 2, From 1st dose to 8 weeks after the last dose if the route is oral, sublingual or intrauterine 3, From 1st dose to 12 weeks or longer, if the route is subcutaneous or intradermal.
		5	Hormone replacement therapy	3	Progestogens	1, From 1st dose to 4 weeks after the last dose if the route is vaginal, intravaginal, cutaneous, nasal or transdermal 2, From 1 st dose to 8 weeks after the last dose if the route is oral, sublingual or intrauterine 3, From 1st dose to 12 weeks or longer, if the route is subcutaneous or intradermal.
		772	Cancer therapies	738	Endocrine antineoplastic therapy	From 1st dose to 12 weeks after the last dose

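### First supplementary analysis: a woman who stops for AE or lack of efficacy and starts a listed VMS drug can fall under both pattern 1 and pattern 3, and the SAP does not say which governs

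*SAP*

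**What the plan says.** **Scenarios.** SAP Table 5-4 gives women who stop for AE or lack of efficacy and then start alternative VMS treatment a hypothetical strategy with the scenario "If participant remained untreated". Table 5-5, pattern 3, repeats this: "Otherwise, if participant initiated an alternative treatment, use the hypothetical strategy under the hypothetical scenario" that no alternative treatment was begun after stopping. Her later data are discarded and re-imputed with indicators of whether she was on randomised treatment at each visit.

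**Pattern 1.** Intake of prohibited medication for any reason is imputed from "Participants, from the same arm, who comply with treatment regimen and have observed data at the time point that requires imputation". The table's footnote defines compliance as having no intercurrent event, so these women are still on study drug. SAP 6.3 says the input holds the affected women and "participants from the reference group, i.e., participants who complied with the randomized treatment".

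**Order.** SAP 5.3.3.1 states: "The imputations will be done sequentially in patterns 1 through 4". The pattern 3 step in 6.3 takes in all participants, including "values that might have been imputed as part of pattern 1 and 2".

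**Drug lists.** Table 6-3 is the "Preliminary list of alternative VMS treatment by drug grouping" and Table 6-4 its counterpart by drug name. Table 6-5 is the "Preliminary list of prohibited concomitant medication by drug grouping" and Table 6-6 its counterpart by name.

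**Precedence.** The only such rule, a footnote to Table 5-5, ranks competing reasons for a temporary interruption.

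**The concern.** Two rules can apply to the same woman and they ask different questions. Pattern 1 asks how she would have done on study drug without the prohibited medication. Pattern 3 asks how she would have done off study drug without rescue. The discard windows differ too: a drug-specific period in pattern 1, everything after the event in pattern 3.

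This analysis exists to remove the influence of rescue. If the choice is left to programming, women who stopped because the drug failed or was not tolerated may be credited with an on-treatment response. Their values would then sit in the pattern 3 input labelled as off treatment and could pull the other off-treatment imputations toward on-treatment values.

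**Working it through.** **1. Do the lists overlap?** Entries of SAP Tables 6-3 and 6-4 checked against Tables 6-5 and 6-6:

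| Alternative VMS entry | Code | Also prohibited? |
|---|---|---|
| Oestrogens | 5 / 2 | Yes, Table 6-5 |
| Progestogens | 5 / 3 | Yes, Table 6-5 |
| SSRI | 111 / 113 | Yes, Table 6-5 |
| OXYBUTIN | 005389 / 02 / 057 | Yes, Table 6-6 |

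The overlap is 4 of 4.

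**2. Can the prohibited-medication event occur after study drug is stopped?** The documents point both ways.
- Yes: SAP 5.1.2 flags events from randomisation to Day 84. SAP 5.2 censors this event at Week 12 or study dropout, not at treatment discontinuation. SAP 6.5.3 sets no on-treatment limit.
- No: SAP 6.5.3 refers back to medications defined in the protocol, and protocol Table 10-4 ends the prohibition 1 week after the last dose. SAP 6.6.5 classes a drug started after the last intake as post-treatment, not concomitant.

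**3. What does literal execution give?** If she is flagged for pattern 1, step 1 of 6.3 fills her values from compliers for the period of drug impact. The pattern 3 step takes those values in, and no later step re-imputes them.

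**4. Size.** The plan gives no figure for this point. The planning inputs used for scale (SAP Table 3-1: SD 4.29, N = 270 per arm, one-sided 0.025) do reproduce the stated power. The t-test gives 77.14%, 98.19% and 99.97% for differences of 1.00, 1.50 and 2.00, against 77.1%, 98.2% and >99.9%.

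Shift in the elinzanetant arm mean = f × D. Here f is the share of the arm affected and D is how much worse the off-treatment imputation is than the complier-based one. Neither is in the documents. Assume f = 0.5% to 5% (1.5 to 15 of 300 women) and D = 1 to 2 hot flashes per day, borrowing the range of planned treatment differences.
- Low: 0.005 × 1 = 0.005 per day
- Middle: 0.02 × 1.5 = 0.03 per day
- High: 0.05 × 2 = 0.10 per day

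Planned standard error of the difference = 4.29 × √(2/270) = 0.37. The high case is 0.10 / 0.37 = 0.27 standard errors; the low case is 0.005 / 0.37 = 0.01.

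**5. Second supplementary estimand.** For AE or lack-of-efficacy stoppers who start rescue, both rules give no change from baseline, so the overlap is harmless. For women who stop for other reasons (SAP 6.5.2 includes subject decision and withdrawal) and then start such a drug, the rules conflict. SAP 5.3.3 and the variable defined in 5.3.3.2 give no change from baseline. Table 5-7, pattern 4, imputes her as if she had not discontinued.

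**The case against.** A reader might infer that the SAP prescribes imputing these women as if they were still taking elinzanetant. It does not. SAP 5.3.3 names discontinuation with alternative VMS treatment separately from prohibited intake, and Tables 5-4 and 5-5 give that group its own scenario. The pattern 3 step refers to unobservable data, which within that pattern can only come from women who start alternative treatment, so the authors evidently expected them there. The stated sequence is an order of imputation, not a rule for assigning women to patterns. All of this stands as evidence of intent. It does not remove the conflict, because pattern 1 covers any reason and nothing takes these women out of it.

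It can also be said that drugs started after the last dose are not prohibited concomitant medication. That reading is available but not settled (step 2). Even on the protocol's own window, a drug started within a week of the last dose is prohibited.

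The size is open to challenge, and rightly. Imputation conditions on a woman's own earlier values, so one who stopped for lack of efficacy carries poor values forward. The borrowed 1 to 2 range is a between-arm difference, not a loss on stopping. A 5% share is 15 women, half of the 30 (10% of 300) assumed to drop out in months 1-3. If fewer than 10 discontinuers have post-discontinuation data at a time point, the indicator is dropped there and the two patterns move closer together.

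That the drug lists are preliminary and reviewed before unblinding does not help: a list review changes the drugs, not the precedence.

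Women who stop for other reasons might seem to raise the same problem in the first supplementary analysis. They do not: pattern 4 is meant to impute them as on treatment, so patterns 1 and 4 differ only in reference group.

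**Conclusion.** The SAP leaves an unresolved conflict between patterns 1 and 3 in the first supplementary analysis. Literal execution of 6.3 may give these women an on-treatment value that contradicts Table 5-4. That goes beyond missing detail, since two stated rules give different values for the same woman.

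The effect is probably small: 0.005 to 0.10 hot flashes per day on assumed inputs, at most about a quarter of the planned standard error. A reader might infer a demonstrated bias toward elinzanetant. The documents do not show one. The same ambiguity exists in the placebo arm, and the direction holds only if stopping elinzanetant loses more effect than stopping placebo, which is plausible but not established. The carry-over into pattern 3 cannot be sized from the documents.

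The primary analysis uses treatment policy throughout and is unaffected. The second supplementary estimand has a separate inconsistency, confined to women who stop for other reasons and then start a prohibited or alternative drug.

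**What to change.** **First supplementary analysis (SAP 5.3.3.1 and 6.3).** State that, from the week in which permanent discontinuation for AE or lack of efficacy is flagged, women who start alternative VMS treatment are assigned to pattern 3 only, with the indicator set to not on treatment, and are left out of pattern 1 from that week. This also keeps complier-based values for them out of the pattern 3 input.

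State also how prohibited drugs not on the alternative list (gabapentin, clonidine and SNRIs, for example) are handled analytically after discontinuation. Without this, removing pattern 1 could leave such women under treatment policy with confounded data.

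**Second supplementary estimand (SAP 5.3.3, 5.3.3.2, Tables 5-6 and 5-7).** Say whether no change from baseline or pattern 4 applies to women who stop for other reasons and then start a prohibited or alternative drug. Do not carry the pattern 3 precedence rule into this estimand: a blanket statement that the discontinuation pattern governs could override its no-change rule.

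**Cost.** A few sentences in the SAP and a small change to the pattern-assignment program, with no new data. SAP 6.5.2 already asks for treatment status to be captured for all discontinuers whatever the reason. The wording should be settled before unblinding.

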### 5.3.3.2 Second Supplementary Analysis

The details of the second supplementary estimand can be found in Table 5–6 and Table 5–7. Similar analysis steps (i.e., imputation, modeling and combining results) as for the first supplementary analysis will be applied to the secondary supplementary analysis (see Section 5.3.3.1).

For the intake of prohibited medication and permanent treatment discontinuation after which participants initiated alternative VMS treatments, the composite strategy will be used to handle the data. The attributes for this estimand are the same as the main estimand except for following:

- Variable: Change in frequency of moderate to severe HF from baseline to Week 12 in the absence of ICEs (i.e. intake of prohibited medication or initiation of alternative VSM treatment after permanent discontinuation of randomized treatment) or no change from baseline otherwise.
- Intercurrent Events (ICEs): see Table 5–6.

